## 5 Study Design

### 5.1.1 Study design

We will conduct a randomized stepped wedge design. This pragmatic design involves a sequential, randomized roll-out of the intervention across 6 participating clinical sites over 3-month intervals or “steps”. Thus, each site receives the intervention. **Table 4** details this approach: 21-month full historical control period followed, sequential roll out of the intervention every 3 months over an 18-month period, then an additional 24 months of full study intervention. A 3-month wash-out period between the end of the historical control collection period and the beginning of the intervention roll-out period is designed to minimize subject crossover contamination. Subjects diagnosed with breast cancer during the washout periods will be excluded from analyses.

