### 5.1.2 Randomization scheme

Consistent with a stepped wedge design with one site implementing the intervention per step, prior to the collection of data in the pre-intervention period, a set of uniform random numbers has been generated for each of the six clusters to assign a starting period for the study intervention. There will be no crossover of patients from usual care to the intervention. That is, patients at each site during the pre-intervention period will experience only usual care and those enrolled after the initiation of intervention will experience the intervention.

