3. Social Determinant of Health (SDOH) Platform systematically identifies barriers to care and links the patient to available resources in the community to address them. The screening/referral system has been built using the Aunt Bertha platform. At time of diagnosis, the navigator will ask patients a series of 17 questions to identify needs categorized into 10 social domains (e.g., transportation, housing, food, paying for utilities). Women will then be referred to local resources aimed at addressing SDOH. These data will be available and stored in the Aunt Bertha platform for use by the patient navigators. At each contact, the navigator will check on the status of referrals and assess whether a woman would like to receive additional referrals for previously identified or new barriers to care. Sites that have a pre-existing platform for identifying and addressing social needs can continue to use their existing systems, and will document assessment and referral details in the shared REDCap registry to make it accessible to navigators at other sites.

As stated in the TRIP study design, there is no control intervention. All controls are historical, thus they represent usual care, prior to implementation of the intervention at each site.

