### 12.3 Statistical Methods

Given the randomized stepped wedge design, we will report our results according to CONSORT guidelines. Our comparative analyses between the intervention and usual care (control) groups will employ the intent-to-treat principle. We will generate descriptive statistics (means, standard deviations, quantiles for continuous variables; counts/percentages for categorical variables) and schematic plots.

We will compare the intervention and usual care groups on salient variables in order to assess balance in the distributions of these variables. Variables found to differ between the study groups will be further evaluated to assess their confounding effects of intervention vs. usual care differences on primary and secondary outcomes. Given the nature of the cluster randomization employed, we will employ statistical analytic methods that take the correlated nature of the data into account.

Our primary analysis will use multiple logistic regression models to compare the proportion of patients with *timely initiation of treatment* across study groups, adjusting for the influence of race, language barriers to care, insurance status (private vs public), and other covariates that may have a significant effect on the outcome and may be unbalanced across the two study groups.

- To examine heterogeneity in intervention effect, exploratory analyses using multiple logistic regression interaction models will examine whether the effect of the TRIP intervention vary by three covariates of interest:
  - patient race
  - patient preferred language
  - insurance status
- Study groups will also be compared on the secondary clinical outcome of *time to initiation of primary cancer treatment* (the number of days from diagnosis to start of treatment) through Kaplan-Meier survival curves (unadjusted analyses) and Cox proportional hazards regression models controlling for cancer site and other covariates (adjusted analysis).
- *Receipt of quality care* will be analyzed through logistic regression.

For the analysis of the rate of missed appointments, patients will differ on the number of scheduled appointments over the study period. The odds of missing an appointment will be analyzed through generalized estimating equation (GEE) logistic regression models for repeated measures (appointments within patient) dichotomous data.

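### Section 12.3 pre-specifies no adjustment for calendar time, although at every site all control patients are diagnosed before all intervention patients

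*Combined protocol and SAP*

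**What the plan says.** Section 5.1.1 sets out a "21-month full historical control period followed, sequential roll out of the intervention every 3 months over an 18-month period", with a 3-month wash-out at each site and a further 24 months of full intervention. Section 5.1.2 adds that "patients at each site during the pre-intervention period will experience only usual care", and section 8 that "All controls are historical, thus they represent usual care, prior to implementation of the intervention at each site". Starts are staggered, so the two conditions overlap in calendar time across sites but never within one.

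Section 12.3 is the whole analysis plan. Its models for the clinical outcomes are:

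- Logistic regression for timely initiation (called primary there), "adjusting for the influence of race, language barriers to care, insurance status (private vs public), and other covariates that may have a significant effect"; the last group is worded in full as "other covariates that may have a significant effect on the outcome and may be unbalanced across the two study groups".
- Cox regression for days to treatment: cancer site and unspecified covariates.
- Logistic regression for quality of care: no covariates named.

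Two general sentences apply to all of them: "Variables found to differ between the study groups will be further evaluated to assess their confounding effects", and "we will employ statistical analytic methods that take the correlated nature of the data into account". No section mentions a secular trend or a time adjustment.

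**The concern.** Randomising the order of roll-out protects a stepped wedge against trend only if the analysis compares patients diagnosed at about the same time. If time is left out, each site contributes a before-after contrast. Improvement that would have happened anyway inflates the estimate, and deterioration hides a real effect. A site effect does not help, because a trend shared by all sites lies within sites. The sentence on correlated data concerns clustering, not trend.

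The only routes for time are the unspecified covariates and the evaluation of variables that differ between groups. Diagnosis date differs by design, so it would qualify for evaluation. Whether it is then kept, and in what form, would be settled after the data are seen. Sections 4.2.1 and 12.3 differ on which outcome is primary; that is a separate matter, and the time term is needed for both.

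**Working it through.** **The plan's own figure.** Section 12.2 needs 2 x 220 x 2.29 = 1,007.6, that is 1,008 patients. This reproduces. The described inputs to the design effect (steps, patients per period, ICC 0.1) do not mention a trend.

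**Layout.** From section 5.1.1 and Table 4, take 21 quarters: 7 of control only, 6 of roll-out and 8 of full intervention, with one wash-out quarter per site. Spread each Table 6 site total evenly over its 20 usable quarters. This reproduces every Table 6 count. For example, Faulkner has 166/20 = 8.3 per quarter, giving 7 x 8.3 = 58 controls and 13 x 8.3 = 108 intervention patients. Dana-Farber has 13 per quarter, giving 156 and 104.

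**Separation in time.** Number the quarters 0 to 20 and the sites i = 0 to 5. Controls at site i fill quarters 0 to 6+i, with mean (6+i)/2. Intervention patients fill quarters 8+i to 20, with mean (28+i)/2. The difference is 11 quarters, or 2.75 years, at every site. Pooled over sites, the mean diagnosis dates are 32.2 months apart. Both conditions are present only in quarters 8 to 11, which hold 33.2 + 31.95 + 10.65 + 67.2 + 21.3 + 52 = 216 of 1,300 patients (17%).

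**Bias.** With site but no time in the model, an ASSUMED drift of 1 point per year gives 1 x 2.75 = 2.75 points of spurious effect, against 81% - 70% = 11. A drift of 11/2.75 = 4 points per year would mimic the whole planned effect.

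**Type I error.** Use variance 0.755 x 0.245 = 0.185 and within-site share 1 - 0.1 = 0.9. Summing (controls x intervention)/(total) over the six sites of Table 6 gives 315.9. The standard error is sqrt(0.185 x 0.9/315.9) = 0.0230; the mixed-model value is 0.0229. At 1 point per year, 0.0275/0.0229 = 1.20, and the chance of exceeding 1.96 in either direction is 22.4%. With an ASSUMED t reference on 4 df it is 15.4%.

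**Other readings of the calendar.** Section 2 gives a 24-month control window and a July 2022 end. Section 5.1.6 has charts abstracted 16-18 months after diagnosis. The layouts below keep the quarterly rates, so totals fall when accrual stops early (with Table 4 controls, to 1,300 x 17/20 = 1,105 or 1,300 x 15/20 = 975).

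| Control window; last diagnosis | Gap, months | Bias per 1 point/year | Type I error, normal | Type I error, t 4 df |
|---|---|---|---|---|
| Table 4; full accrual | 32.2 | 2.75 | 22.4% | 15.4% |
| Table 4; early 2021 | 27.5 | 2.37 | 15.5% | 11.3% |
| Table 4; mid-2020 | 24.3 | 2.12 | 11.7% | 9.1% |
| 24 months excluding wash-out; full | 29.7 | 2.52 | 18.2% | 12.9% |
| 24 months including wash-out; full | 28.5 | 2.42 | 16.3% | 11.8% |
| 24 months including wash-out; early 2021 | 23.8 | 2.05 | 11.8% | 9.2% |
| 24 months including wash-out; mid-2020 | 20.6 | 1.81 | 9.4% | 7.7% |

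The rows ending in early 2021 or mid-2020 are those that fit the stated end date.

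**Cross-check on the logistic scale.** This used 2,000 simulated trials on the full layout with site fixed effects, an ASSUMED 70% baseline and an ASSUMED between-site SD of 6 points. With no time term, type I error was 18.6% at 1 point per year. With linear or quarter terms it was 4.0-5.7%.

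**Would the existing clauses let time in?** On the full layout at 1 point per year, normal reference:

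- Keep linear time if p<0.05: kept in about 10% of trials; type I error about 23% (20% in the logistic simulation).
- Keep it if the treatment estimate moves by more than 10%: kept in about 95%; type I error about 7%.
- Keep it if the estimate moves by more than 20%: kept in about 91%; type I error about 9%.

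All three rules are ASSUMED, because the plan states none.

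**Power with time in the model.** For 11 points at N = 1,300 and ICC 0.1, on the difference-in-proportions scale:

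- Linear term: SE 0.0474; 0.11/0.0474 = 2.32; power 64% (normal) or about 43% (t, 4 df).
- Quarter effects: SE 0.0685; 0.11/0.0685 = 1.61; power 36% or about 24%.

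**The case against.** The best reply is that the plan already covers this. Diagnosis date is bound to differ between groups, so it would be evaluated as a confounder. If evaluation means asking whether the treatment estimate moves, time would nearly always be kept and type I error would stay near 7-9%. This has force. A reader might infer that the plan excludes time, or that its covariate clauses cannot repair the bias. The text supports neither. The neighbouring clause, however, speaks of a significant effect on the outcome and fits a significance screen equally well; under that rule the protection largely fails. What stands is that protection depends on an unstated rule.

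Second, no trend is documented. That is correct: every error rate above depends on an assumed drift. A reader might point to section 9.4.1, where Boston Medical Center (448 of 1,300 planned patients) used a comparable social-needs platform before roll-out, as evidence of drift. No start date is given. If the platform predates the control period it causes none, so it is not a demonstrated source.

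Third, the 22% figure comes from the layout that fits the calendar least well. It runs to about October 2021, and abstraction 16-18 months later would fall in 2023. It does match Table 6 exactly, but it should be read as the upper end.

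Fourth, quarter effects in every model would be a preference. They cost the most power, and the quality measures apply only to subsets of women: Tufts averages 71/20 = 3.6 patients per quarter before any subsetting. This also stands.

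**Conclusion.** The point holds as a failure to pre-specify. The design makes time the main threat to the effectiveness estimate, and section 12.3 leaves its handling to an undefined choice. With site but no time in the model, each assumed 1 point per year of drift adds about 1.8 to 2.8 points of bias to a planned 11. Type I error is then about 9-22% (normal) or 8-15% (t, 4 df). On layouts consistent with the July 2022 end date and the abstraction window it is about 9-16% or 8-11%. These figures assume even accrual within site, linear drift common to all sites and ICC 0.1.

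A reader might infer that the trial's result is biased, or that its false-positive rate is 22%. Neither follows, because no trend is reported and the final model is not fixed. The section 12.2 statement that 1,300 patients are more than enough is not shown for a time-adjusted analysis. The power figures are approximate, since section 12.2 is framed as a log-rank test.

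**What to change.** In section 12.3:

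- Pre-specify adjustment for calendar time of diagnosis and for clinical site in the primary logistic and Cox models. Clinical site should replace cancer site, which is constant in a breast-only trial.
- Do the same in the quality-of-care models, in a form their subset sizes can support.
- State and justify the form of the time term in advance, for example 3-month period effects or a linear or smooth term, and name an alternative form as a sensitivity analysis. A linear term protects only against roughly linear drift.
- State inference suited to six clusters.

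In section 12.2, restate power under that model and revise the adequacy statement.

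No new data are needed: diagnosis date and institution are already collected (section 10.1.5). The cost is lower stated power: about 64% (linear) or 36% (quarter effects) for 11 points under a normal reference, and less with a small-sample t reference. The higher power of a model without time is bought by assuming that there is no drift.

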## 2 Protocol Summary

Title:	Translating Research into Practice: TRIP
Population:	Newly diagnosed breast cancer patients 18 years or older who live within a 35 mile radius of Boston, MA and have any of the following risk factors for delays in care: are Black and/or Hispanic race/ethnicity, do not speak English as their primary language, and/or have only public insurance or are uninsured at the time of diagnosis.
Intervention:	Implementation of three evidence-based tools that facilitate timely treatment: (a) shared patient registry to identify and track patients from diagnosis through treatment; (b) systematic screening for SDOH with a web-based platform to support a personalized referral plan to regional resources; and (c) one-on-one patient navigation services. The integration of these tools into one integrated model of care will become the standard of care at each participating site, with the aim to improve the quality and timeliness of care delivery, for minority and/or low-income women with breast cancer.

---

Objectives:	The main study objective is to implement an evidence-based integrated care delivery model (patient registry, screening for social determinants of health (SDOH) and patient navigation) across six health systems in Boston and evaluate the impact on clinical care outcomes among minority, low-income women with breast cancer. The primary objective is to test the clinical effectiveness of the intervention, as measured by the time to first cancer treatment and receipt of guideline concordant care. The secondary objective is to evaluate the implementation of the intervention (fidelity to intervention protocol, local adoption/sustainability, and acceptability).

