**5.1.4.1 Table 6. Expected Recruitment Projections**

Sites	Control	Intervention	Total
Boston Medical Center (BMC)	224	224	448
Beth Israel Deaconess (BIDMC)	85	128	213
Brigham and Women's/ DFCI	156	104	260
Faulkner Hospital (BWFH)	58	108	166
Tufts Medical Center (TMC)	32	39	71
Massachusetts General Hospital (MGH)	78	64	142
Total	633	667	1300

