# **7 Study Subject Selection**

## **7.1 Subject Inclusion Criteria**

In order to be eligible to participate in this study, an individual must meet all of the following criteria:

Eligibility criteria: All women with breast cancer diagnosed during the study period will be eligible for inclusion if they meet three study criteria:

1. are an adult female 18 years of age or older;
2. reside within a 35 mile radius of Boston;
3. have any of the following risk factors for delays in care:
  - a. Black and/or Hispanic race/ethnicity
  - b. do not speak English as their primary language and/or
  - c. have only public insurance or are uninsured at the time of diagnosis.

Women who do not meet all three criteria will be excluded from the study. In some cases it is possible, due to the scope of the patient navigator's responsibilities that patients who are ineligible will be entered into the Registry. As the registry is HIPAA compliant and these individuals will be excluded from compiled data sets, the study team does not perceive this to be a major risk.

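### The one covariate named for the Cox model, cancer site, is constant in a breast-only trial, and no model in Section 12.3 names clinical site, although the projected site mix differs by arm

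*Combined protocol and SAP*

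**What the plan says.** The Cox analysis of days from diagnosis to first treatment is described in Section 12.3 as "Cox proportional hazards regression models controlling for cancer site and other covariates (adjusted analysis". Cancer site is the only covariate named; the rest are left open.

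The population is breast cancer only. The Protocol Summary gives it as "Newly diagnosed breast cancer patients 18 years or older", and Section 7.1 says "All women with breast cancer diagnosed during the study period will be eligible for inclusion if they meet three study criteria".

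The randomised unit is the hospital. Section 5.1.2 states that "a set of uniform random numbers has been generated for each of the six clusters" to fix the starting periods.

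Three other sentences in 12.3 bear on site:
- The logistic model, which 12.3 calls the primary analysis, is specified as "adjusting for the influence of race, language barriers to care, insurance status (private vs public), and other covariates". Clinical site is not listed.
- On imbalance: "Variables found to differ between the study groups will be further evaluated to assess their confounding effects".
- On clustering: "we will employ statistical analytic methods that take the correlated nature of the data into account". No cluster term or method is attached to this sentence. The only correlated-data method named in 12.3 is GEE for missed appointments, where the cluster is the patient.

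**The concern.** In a stepped wedge, the roll-out order ties hospital to arm. A hospital that starts early contributes relatively more intervention women, and one that starts late relatively more controls. If hospitals differ in how fast they treat, a comparison without a site term mixes those differences into the intervention effect, in either direction.

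The Cox sentence looks as if it deals with this, because it names a site variable. Read literally, that variable does nothing. This matters because Section 4.2.1 makes time to treatment the primary outcome and says the study is powered on it, and the sample size in 12.2 starts from a log rank test. Section 12.3 labels the same analysis secondary. That inconsistency is a separate matter, but on either label the model needs a term that works.

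**Working it through.** **1. The plan's own figures.** Table 6 ("Expected Recruitment Projections", Section 5.1.4) adds up: controls 58 + 85 + 32 + 224 + 78 + 156 = 633; intervention 108 + 128 + 39 + 224 + 64 + 104 = 667; total 1,300. The minimum sample size in 12.2 also reproduces: 2 × 220 × 2.29 = 1,007.6, rounded up to 1,008. The design effect of 2.29 could not be re-derived, because its formula and the per-period numbers are not given.

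**2. A constant in a Cox model.** Give every woman the same cancer-site value c, with coefficient γ, and let x be her other terms with coefficients β. Each factor of the partial likelihood is exp(βx + γc) / Σ exp(βxⱼ + γc). The factor exp(γc) cancels, leaving exp(βx) / Σ exp(βxⱼ). So γ cannot be estimated and the intervention coefficient is unchanged.

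**3. Site mix by arm.** Counts are from Table 6. The order is the roll-out order in Table 4, taking the combined Brigham/DFCI row as the Dana-Farber cluster. The difference d is intervention share minus control share.

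| Site | Control, n (% of 633) | Intervention, n (% of 667) | d, points |
|---|---|---|---|
| Faulkner | 58 (9.2) | 108 (16.2) | +7.0 |
| Beth Israel Deaconess | 85 (13.4) | 128 (19.2) | +5.8 |
| Tufts | 32 (5.1) | 39 (5.8) | +0.8 |
| Boston Medical Center | 224 (35.4) | 224 (33.6) | −1.8 |
| Massachusetts General | 78 (12.3) | 64 (9.6) | −2.7 |
| Brigham/DFCI | 156 (24.6) | 104 (15.6) | −9.1 |

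The positive differences sum to 13.6 points: that share of one arm would have to change hospital to match the other. Within a site, the intervention share runs from 104/260 = 40.0% to 108/166 = 65.1%.

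**4. What mix alone could do.** With no true effect, the crude arm difference in timely treatment is Σ d × (site rate). The documents give no site rates, so the rates below are assumptions. The planned difference is 81% − 70% = 11 points.

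- *Only Brigham/DFCI differs, by 10 to 30 points.* 9.05 × 0.10 = 0.9 and 9.05 × 0.30 = 2.7 points, or 8% to 25% of 11.
- *Rates evenly spaced over 20 points, falling in roll-out order.* 7.03 × 0.20 + 5.76 × 0.16 + 0.79 × 0.12 − 1.80 × 0.08 − 2.73 × 0.04 − 9.05 × 0 = 2.2 points. Because d falls steadily in this order, this is the maximum over all orderings. The maximum is 1.1 points for a 10-point spread and 3.3 for a 30-point spread.
- *The ICC of 0.1 in 12.2, read as between-site variance at a 70% rate.* Between-site SD = √(0.1 × 0.7 × 0.3) = 14.5 points. With d as proportions, √(Σd²) = 0.133, so the SD of the mix-only shift is 14.5 × 0.133 = 1.9 points.

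**5. Do the general sentences supply a site term?** The open-ended list of covariates names nothing. The imbalance check depends on the data and on an unstated choice of variables, whereas the site imbalance is built in by design and known now. The clustering sentence would be satisfied by a robust variance, which changes the standard error and leaves the point estimate, with any mix effect in it, where it was.

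**The case against.** The strongest reply is that the plan does not rule site out. The Cox sentence goes on to further covariates, the imbalance check covers primary and secondary outcomes and could be triggered by the imbalance shown above, and there is an explicit commitment to respect the clustering. The documents also use the word site mostly for hospitals, so the phrase may be a slip, in which case the intended model already adjusts for hospital and one word needs correcting. This stands. A reader might infer that clinical site is left unadjusted; the documents do not support that. They leave adjustment for site unspecified.

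The second reply concerns size. The shifts are on the proportion scale, rest on assumed site rates, and in the gradient case use the least favourable ordering. Starting periods were assigned by random numbers, so an alignment of hospital speed with roll-out order would be chance. This also stands. A reader might take 8% to 25% as the bias of the Cox result; it is not, and no hazard-ratio bias can be derived from the documents.

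The third reply is that a point confined to the Cox sentence is too narrow, since the logistic model called primary lacks a site term as well. That is right, and the change should cover both. It is also right that the Kaplan-Meier curves, which the plan labels unadjusted, need no alteration.

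What the replies do not remove is that the one covariate named does nothing as written and that no sentence commits the analysis to a site term. Even read as a slip, the phrase does not say how site would enter the model.

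**Conclusion.** The Cox specification is wrong as written in its one named covariate, and the handling of clinical site is open in every model in 12.3. The difference in site mix between arms comes from the plan's own projections and rests on no assumption beyond matching the Brigham/DFCI row to the last roll-out site. The consequence is modest: about 1 to 3 points of crude difference in timely treatment against a planned 11, if sites differ by 10 to 30 points, with the sign unknown. It is an illustration on the proportion scale. The correction should be made before analysis because the imbalance is foreseeable and the remedy is cheap.

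**What to change.** In Section 12.3, replace cancer site with clinical site and state how it enters: a Cox model with baseline hazard stratified by the six randomised sites (a site fixed effect is an acceptable alternative), with calendar period of diagnosis as a covariate, because the stepped-wedge roll-out ties arm to calendar time. Name the same site term in the logistic model for timely treatment that 12.3 calls primary. The Kaplan-Meier curves can stay as the labelled unadjusted description.

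The cost is a sentence for each model. No new data are needed: Section 10.1.5 already requests primary institution and date of diagnosis for historical controls, and the overview of patient identifying elements in Section 10.1 lists institution of care and date of diagnosis among the abstracted chart data. Calendar period should be kept as a derived variable in the coded analytic file. No stated sample-size figure has to change.
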